9.1.3 Adverse Event of Special Interest

An adverse event of special interest (AESI; serious or non-serious) is one of scientific and medical concern specific to the Sponsor's product or program, for which ongoing monitoring by the Sponsor may be warranted. Such an event should be entered into EDC in a timely manner and if applicable, reported as an SAE. Depending on the nature of the event, rapid communication by the trial Sponsor to other parties (eg, regulators) might also be warranted (based on CIOMS VI).

For VIS410, the AESIs include the following:

- Abdominal cramping
- Diarrhea/Loose stool
- Nausea
- Vomiting
- Pruritus
- Rash
- Hypotension
- Throat tightening
- Trouble breathing or wheezing

9.1.4 Serious Adverse Events

A serious adverse event (SAE) is any untoward medical occurrence that at any dose meets any of the following conditions:

- Results in death.
- Is life-threatening, ie, the patient was at risk of death at the time of the event (eg, ventricular fibrillation and anaphylaxis). The term does not refer to an event which hypothetically might have caused death if it were more severe.
- Requires inpatient hospitalization or prolongation of existing inpatient hospitalization. Hospitalization refers to an overnight admission into hospital for the purpose of investigating and/or treating the AE. Hospitalization for an elective procedure, or routinely scheduled treatment for a preexisting condition that has not worsened, is not an SAE.
- Results in persistent or significant disability/incapacity, ie, causing substantial disruption of the patient's ability to conduct normal life.
- Is a congenital anomaly/birth defect.
- Is medically significant, ie, may not be immediately life-threatening or result in death or hospitalization but may jeopardize the patient's health or may require intervention to prevent one of the above outcomes. Examples of such events are intensive treatment in an emergency room or at home for allergic bronchospasm, blood dyscrasias, or convulsions that do not result in hospitalization or development of drug dependency or drug abuse.

9.1.5 Discontinuation Due to an Adverse Event

Study drug may be discontinued due to an AE at the discretion of the subject and/or the Investigator. Subjects in whom study drug is discontinued will undergo the early withdrawal procedures listed in Section 6.1.5.

9.1.6 Unlisted (Unexpected) Adverse Events

An AE is considered unlisted if the nature or severity is not consistent with the applicable product reference safety information (Investigator's Brochure).⁸

9.1.7 Suspected Unexpected Serious Adverse Reactions

Suspected unexpected serious adverse reactions (SUSARs) are SAEs that are unexpected and judged by the Investigator or Sponsor to be related to the study treatment administered.

The Sponsor or designee will report SUSARs and other applicable SAEs to the appropriate regulatory authorities, central ethics committees (ECs)/institutional review boards (IRBs)/ and Investigators as required, according to local law.

9.1.8 Treatment-Emergent Adverse Event

A treatment-emergent adverse event (TEAE) is defined as any event not present prior to the initiation of the treatments or any event already present that worsens in either intensity or frequency following exposure to the treatments.

9.2 Grading of Adverse Event Intensity

Each AE must be graded on a 4-point scale (Grades 1-4) of increasing intensity according to the Division of Microbiology and Infectious Diseases (DMID) Adult Toxicity Table presented in Appendix 14.3.

Criteria in the DMID table are generally grouped by body system, ie, hematology, chemistries, enzymes, urinalysis, cardiovascular, respiratory, GI, neurological, musculoskeletal, skin, and systemic.

For abnormalities not specifically listed in the DMID Table (Appendix 14.3), a guide for estimating severity grade (mild, moderate, severe, life-threatening) is provided:

- Grade 1: Mild transient or mild discomfort (< 48 hours); no medical intervention/therapy required
- Grade 2: Moderate/mild to moderate limitation in activity—some assistance may be needed; no or minimal medical intervention/therapy required
- Grade 3: Severe/marked limitation in activity, some assistance usually required; medical intervention/therapy required, hospitalizations possible
- Grade 4: Life-threatening; Extreme limitation in activity, significant assistance required; significant medical intervention/therapy required, hospitalization or hospice care probable

Note: The semi-colon within the description of the grade indicates ‘and’.

Any clinical event deemed by the clinician to be serious or life-threatening should be considered an SAE.

9.3 Causality Assessment

The following binary choice will be used by the Investigator to describe the causality assessment with the test treatment:

- Reasonable possibility: There is evidence to suggest a causal relationship between the test treatment and the AE (eg, AE is uncommon and known to be strongly associated with drug exposure or is uncommon in the study population, but not commonly associated with drug exposure).
- No reasonable possibility: There is no evidence to suggest a causal relationship between the test treatment and the AE.

9.4 Action Taken Regarding Investigational Product

The action taken toward the study drug must be described as one of the following:

- Permanently discontinued
- Stopped temporarily
- Modified infusion rate
- No action Taken
- Not applicable

9.5 Outcome

The outcome of each AE must be rated as one of the following:

- Recovered/resolved
- Recovering/resolving
- Not recovered/not resolved
- Recovered with sequelae/resolved with sequelae
- Fatal
- Unknown

9.6 Recording Adverse Events

All (S)AEs occurring during the clinical investigation must be documented in the EDC system from the time of dosing with any study treatment through Day 56.

Whenever possible, diagnoses should be given when signs and symptoms are due to a common etiology (eg, skin erythema, induration, and edema should be reported as “cellulitis”).

Investigators must record their opinion concerning the relationship of the (S)AE to the study drug in the EDC system. All measures required for (S)AE management must be recorded in the source documents and reported according to the Sponsor’s instructions.

All (S)AEs occurring at any time during the study (including the follow-up period) will be followed by the Investigator until satisfactory resolution (eg, value back to baseline value) or stabilization or until final database lock. If necessary, in order to obtain additional information to ensure safety to the subject, additional blood and urine samples may be taken at the discretion of the Investigator. Certain long-term AEs related to therapy cannot be followed until resolution within the setting of this study. In these cases, follow-up will be the responsibility of the treating physician.

9.7 Reporting Procedures

9.7.1 Reporting Serious Adverse Events

All SAEs, irrespective of the circumstances or suspected cause, must be reported on a Serious Adverse Event Form by the Investigator to the Sponsor or designee within 24 hours of their knowledge of the event, preferably by email.

Contact details for reporting SAEs:

The Serious Adverse Event Form should include a clearly written narrative describing signs, symptoms, and treatment of the event, diagnostic procedures, as well as any relevant laboratory data and any sequelae, in order to allow a complete medical assessment of the case and independent determination of the possible causality.

Follow-up and outcomes should be reported for all subjects that experience an SAE.

It is critical that the information provided on the Serious Adverse Event Form matches the information recorded in the EDC system for the same event. In addition, the same information is to be recorded in the source documents.

Copies of additional reports and documents should be sent when requested and applicable. Follow-up reports relative to the subject's subsequent course must be submitted to the CRO until the event has subsided or, in case of permanent impairment, until the condition stabilizes.

9.7.2 Reporting SAEs to Competent Authorities/Ethics Committees

Visterra or designee is responsible for appropriate reporting of AEs to the regulatory authorities. Visterra or designee will also report to the Investigator all SAEs that are unlisted (unexpected) and associated with the use of the study drug. The Investigator must report these events to the appropriate independent ethics committee/institutional review board (IEC/IRB) that approved the protocol, unless otherwise required and documented by the IEC/IRB.

Visterra or designee will be responsible for unblinding and submitting SUSARs involving VIS410/placebo to the applicable regulatory authorities according to International Conference on Harmonisation (ICH) guidelines. In addition, Visterra or designee will be responsible for the submission of safety letters to the central IEC/IRB and to participating Investigators of all SUSARs involving VIS410 according to applicable regulations. For clinical sites that use a local

IEC/IRB, it is the responsibility of the Investigator to promptly notify the local IEC/IRB of all unexpected serious adverse drug reactions involving risk to human subjects.

After termination of the clinical study (determined as LSLV), any unexpected safety issue that changes the risk-benefit analysis and is likely to have an impact on the subjects who have participated in it, will be reported by Visterra or designee as soon as possible to the competent authority(ies) concerned together with proposed actions.

9.7.3 Reporting a Pregnancy

Subjects should not become pregnant during the study.

Pregnancy is not an AE; however, the Investigator must report any pregnancy which occurs in a female subject or the female partner of a male subject up to 60 days after last dose of VIS410/placebo by emailing the Pregnancy Notification Form to the Sponsor or designee within 24 hours of the study site staff becoming aware of the pregnancy. The Investigator will also follow up with the subject to determine the outcome of the pregnancy and any fetal or neonatal sequelae will be obtained and documented. The Investigator or study site staff must report the outcome of the pregnancy to the Sponsor or designee.

Contact details for reporting Pregnancy:

[REDACTED]

Congenital abnormalities and birth defects in the offspring of male or female subjects should be reported as an SAE if conception occurred during the study treatment period or in the 60-day period after the last dose of VIS410/placebo.

10.0 STATISTICAL METHODS

Further details of the statistical methodology, in addition to those described below, will be described in the statistical analysis plan (SAP). The SAP will be prepared and finalized before database lock and analysis of the data. Additional efficacy analyses including, but not limited to, subgroup efficacy analysis will be specified in the SAP.

10.1 Determination of Sample Size

The study is exploratory in nature, and is not powered to demonstrate significant differences between treatment groups in primary or secondary outcome measures. The protocol intent is to collect sufficient information to identify the most appropriate candidate endpoints for subsequent Phase 3 study evaluation from among the primary and secondary endpoints described below. Statistical significance testing will therefore be used to assess the relative strength of evidence of the primary and secondary endpoints, to provide reasonable assurance that the endpoints chosen for a confirmatory Phase 3 trial will elucidate treatment differences between VIS410 plus oseltamivir versus oseltamivir alone.

10.2 Randomization and Blinding

An IWRS will be used to allocate the randomized treatments to subjects with stratification by presence or absence of positive pressure ventilation (PPV) at baseline. Pharmacists must obtain the status of the subject relative to PPV at baseline via query, and this data must be input into the IWRS prior to randomization. The randomized treatment assignment will be transferred electronically for integration with the clinical study data at the appropriate time.

PPV includes any respiratory assistance using a mechanical ventilation device and can be either invasive or noninvasive ventilation. Invasive PPV includes intubation with endotracheal tube with mechanical ventilation (most common) or tracheostomy with mechanical ventilation. Noninvasive PPV includes use of facemask, nasal plugs, or nasal mask with mechanical ventilation. The devices are named according to the type of mechanical ventilation given continuous positive airway pressure (CPAP) or bi-level positive airway pressure (BiPAP).

Randomization will be used to avoid bias in the assignment of subjects to treatment, to increase the likelihood that known and unknown subject attributes (eg, demographic and baseline characteristics) are evenly balanced across treatment arms.

The maintenance of the study blind is critical for an unbiased assessment of the safety and efficacy of the study drug. All study staff that evaluate subjects and render decisions regarding subject care will remain blinded to the study treatment each subject receives.

The designated study site pharmacist or designee will remain unblinded. Also, unblinded clinical research associates will handle study drug accountability.

The study will be conducted in a double-blind manner. The CRO, site study personnel, and Visterra personnel will not be aware of which treatment (VIS410 or placebo) the subjects have been given. Subjects will not be aware of which treatment they have been administered.

Subjects will be randomized 1:1:1 to receive VIS410 2000 mg, VIS410 4000 mg, or placebo over a 2-hour infusion with pretreatment regimen of PO or IV diphenhydramine 50 mg plus either ibuprofen 400 mg PO or acetylsalicylic acid 320-325 mg PO approximately 60 minutes before IV infusion of VIS410/placebo.

Allocation of each subject to a given treatment sequence will be described in a randomization schedule prepared by Visterra or designee. The randomization will be balanced using randomly permuted blocks across the treatment groups. Based on this randomization code, the site's unblinded pharmacist or trained designee will prepare and dispense VIS410/placebo.

The randomization schedule will not be available to the subjects, Investigators, blinded monitors, or employees of the clinical center involved in the management of the study before unblinding of the data, unless in case of emergency.

The Sponsor's clinical team will also be blinded during the study, as they will not have direct access to the randomization schedule. The CRO personnel performing data management and statistical activities will receive a copy of the randomization schedule during database lock. Other team members will not have access to any data that could lead to unblinding.

Unblinding of the individual subject's treatment (via IWRS) by the Investigator should be limited to medical emergencies or urgent clinical situations in which knowledge of the subject's study treatment is necessary for clinical management. In such cases, the Investigator is encouraged to contact the Medical Monitor to discuss and agree to the need for unblinding to occur. In situations in which the Investigator has tried, but is unable to reach the Medical Monitor, they should use their best judgment, based on the nature and urgency of the clinical situation, and may proceed with unblinding without having successfully reached and discussed the situation with the Medical Monitor.

Once a subject's treatment assignment has been unblinded, the Medical Monitor should be notified within 24 hours of unblinding of the treatment, without revealing the study treatment. Information relating to unblinding (eg, reason and date) shall be clearly recorded in the subject's study file, as part of relevant standard operating procedures. In addition, the Investigator should consider whether the clinical event prompting unblinding should be considered an SAE, according to the regulatory definitions or criteria for SAEs, and if so, submit an SAE report to Visterra or designee. If the code is broken by the Investigator or by someone of his/her staff, the subject must be withdrawn from the study and must be followed as appropriate.

Visterra or designee will also unblind any SAE reports that are serious, unexpected, and considered to be related to investigational product, in accordance with safety reporting guidance and regulations. If the code is broken by the Sponsor for safety reporting purposes, the subject

may remain in the study. To maintain study blinding, the infusion bag will be covered by an opaque sleeve in the pharmacy.

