11.3 Subject Withdrawal from Study

Subjects have the right to withdraw from the study at any time for any reason, including personal reasons. A subject can withdraw without giving a reason. The Investigator should however try to find out why a subject has withdrawn from the study and document the reason for withdrawal.

Subjects must be withdrawn from the study in the event of:

- Withdrawal of informed consent
- Failure of the subject to comply with the protocol requirements or to cooperate with the Investigator
- For safety reasons, it being in the best interest of the subject that he/she be withdrawn, in the Investigator's opinion

In the event that a subject is withdrawn from the study, the study monitor and Sponsor should be informed. In case of withdrawal due to an SAE (for details on AE reporting see Section 9.7), the Sponsor should be notified within 24 hours. In case of withdrawal for other reasons, the Sponsor should be notified within 2 days of the event.

If there is a medical reason for withdrawal, the subject will remain under the supervision of the Investigator until satisfactory health has returned.

Subjects who are withdrawn from the study prior to completion of the scheduled study procedures for any reason (AE, withdrawal of consent, etc.) should be invited to complete the assessments as much as possible. As long as the subject consents, all relevant assessments of the

day on which the subject withdrew from the study should be completed, at least those related to safety. In case of an AE, the appropriate follow-up will be performed.

VIS410/placebo assigned to a withdrawn subject must not be assigned to another subject. Subjects withdrawn from the study will not be replaced.

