### **9.1 Primary Efficacy Analysis – Day 7 Ordinal Scale Status**

The ordinal scale outcomes will be measured daily from Day 1 (Baseline) through Day 14 using the seven-level hierarchical scale with the classifications presented in the table below. The clinical outcomes therein are ordered from the worst clinical outcome to the best clinical outcome in descending order. For each day, subjects will be classified by the worst clinical

January 17, 2019

outcome for which they qualify. The number and percentage of subjects in each treatment group with each classification will be summarized for each day from Day 1 through Day 14, inclusive. For subjects who die prior to Day 7, the score of 7 will be carried forward through Day 14. If a subject is missing an ordinal scale value but is bracketed by the same values on immediately preceding and subsequent days, the value of the missing day will be imputed to be the same as the immediately preceding and subsequent days. If a subject is missing baseline ordinal scale values from Day 1, baseline values will be set to the Day 2 score. If subjects are missing Day 1 and Day 2, the baseline value will not be imputed. No other data will be imputed.

Clinical Outcome	Score
Death	7
ICU stay with mechanical ventilation	6
ICU stay without mechanical ventilation	5
Non-ICU hospitalization with supplemental oxygen	4
Non-ICU hospitalization without supplemental oxygen	3
Discharge with partial resumption of normal activities	2
Discharge with full resumption of normal activities	1

For use in overall summary statistical presentations, the ordinal categories will be assigned decreasing integer scores, with death a score of 7 and discharge with full resumption of normal activities a score of 1. Frequencies of ordinal scores at each visit will be generated and evaluated by proportional odds ratio analysis, as implemented by logistic regression, including a test of the proportional odds assumption and generation of common odds ratios. For this analysis, the reference response category will be 1= Discharge with full resumption of normal activities with the remaining response categories in numeric sequence to worst (7=Death). Additional exploratory analyses may be conducted to obtain a more complete understanding of the relationship of treatment to the ordinal response.

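### Forced study withdrawal after an investigator code-break may leave Day 7 ordinal scores missing for reasons linked to outcome

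*Protocol*

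**What the plan says.** **Code-break.** Under Protocol 10.2, unblinding of an individual subject "by the Investigator should be limited to medical emergencies or urgent clinical situations". The rule that follows is: "If the code is broken by the Investigator or by someone of his/her staff, the subject must be withdrawn from the study". The sentence goes on to require suitable follow-up, but what that follow-up contains is not stated. The same section treats a sponsor code-break differently: "If the code is broken by the Sponsor for safety reporting purposes", the subject is allowed to stay.

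**Withdrawal in general.** Protocol 11.3 lists among its mandatory grounds "Failure of the subject to comply with the protocol requirements or to cooperate with the Investigator". It says that subjects withdrawn early for any reason "should be invited to complete the assessments as much as possible". The firmer request covers only the day of withdrawal, with safety assessments as the minimum. Withdrawn subjects are not replaced.

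**Treatment and endpoint.** VIS410 or placebo is one infusion on Day 1 (Protocol 4.1). The primary endpoint is the seven-level ordinal score on Day 7, recorded daily to Day 14.

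**Missing scores.** Protocol 10.5 leaves missing data to the SAP. SAP 9.1 carries a death score forward, fills a gap when the days on either side have the same score, and sets a missing Day 1 to the Day 2 score. It then closes the list: "No other data will be imputed". SAP 5.1.3 keeps a dosed, influenza A-confirmed subject in the MITT population whatever happens later.

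**The concern.** The rule ends study participation in the cases where the outcome is most likely to be poor. A subject unblinded in an emergency on, say, Day 3 must be withdrawn, and nothing requires that the Day 7 score still be recorded. If it is not, a surviving subject counts in the MITT population but contributes nothing to the Day 7 proportional-odds model.

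This sits badly with Protocol 10.3, which justifies the MITT population by the wish to keep the benefits of randomization and avoid bias from subjects being lost non-randomly.

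The trial is exploratory, but its p-values are meant to help choose Phase 3 endpoints (Protocol 10.1, SAP 2.2). A shift created by missing scores could mislead that choice without ever reaching significance.

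**Working it through.** **No figure to reproduce.** The current documents state no power, effect size, dropout rate or expected number of code-breaks. The only arithmetic in the plan is 3 × 40 = 120, which agrees.

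**Step 1: trace one subject through the rules.**
1. Infusion completed on Day 1; emergency and investigator code-break before Day 7.
2. Protocol 10.2: withdrawal from the study is compulsory, not merely from study drug.
3. Protocol 11.3: later assessments are invited, not required.
4. SAP 9.1: the subject is alive, so there is no death score to carry forward. There is no later score to bracket the gap. The Day 1 rule does not apply. The Day 7 score stays missing.
5. SAP 9.1 plans sensitivity analyses for ICU stays not driven by disease severity, and SAP 9.2.1 plans one excluding death from the AUC. Neither addresses a missing Day 7 score.

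**Step 2: precision.** If a fraction d of an arm of 40 is lost, the standard error rises by the factor 1/√(1 − d). For an assumed d of 2.5%, 5% or 10%, this leaves 39, 38 or 36 subjects and raises the standard error by 1.3%, 2.6% or 5.4%. Precision is not the issue.

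**Step 3: bias.** Assumed inputs, none of them from the documents:
- The same Day 7 distribution in every arm, per 40 subjects: 6, 12, 6, 7, 3, 4, 2 for scores 1 to 7. The true common odds ratio (OR) is 1.00.
- Lost subjects all have score 6 (ICU with mechanical ventilation) and all come from VIS410.

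The model is logit P(score ≥ k) = α_k + β × (VIS410), with OR = exp(β) for a worse score.

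| Lost from VIS410 | One arm, 40 vs 40: OR (p) | Pooled, 80 vs 40: OR (p) | Same loss in both arms of 40: OR |
|---|---|---|---|
| 0 | 1.00 | 1.00 | 1.00 |
| 1 | 0.94 (0.87) | 0.97 (0.93) | 1.00 |
| 2 | 0.88 (0.74) | 0.94 (0.85) | 1.00 |
| 3 | 0.82 (0.61) | 0.91 (0.78) | 1.00 |
| 4 | 0.76 (0.49) | 0.88 (0.70) | 1.00 |

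**Hand check.** Cut the scale at score 4 or worse. Placebo has 7 + 3 + 4 + 2 = 16 subjects at or above the cut and 24 below. Losing m such subjects from one VIS410 arm gives an OR of [(16 − m)/24] ÷ [16/24] = (16 − m)/16. For m = 1 to 4 this is 0.94, 0.88, 0.81, 0.75. For the pooled group it is (32 − m)/32 = 0.97, 0.94, 0.91, 0.88. Both agree with the fitted values to within 0.01.

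**The case against.** **Protecting blinded assessment.** Protocol 10.2 wants everyone who evaluates subjects to remain blinded. A sponsor unblinding for safety reporting need not reach the bedside; an investigator code-break does. Some scale levels depend on judgement, such as ICU placement and partial versus full resumption of activities. So the different treatment of the two code-breaks is not in itself a contradiction, and the rule has an understandable purpose. That stands. It does not require the score to go uncollected: a score recorded after unblinding can be flagged and set aside in a sensitivity analysis, whereas a score never recorded cannot be recovered.

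**Is the Day 7 score actually lost?** A reader might infer that it is. The documents do not say so. Follow-up of some kind is required, assessments are invited, and after a medical withdrawal the subject stays under the investigator's supervision until recovered (Protocol 11.3). Protocol 6.1.5 encourages early-termination assessments. Loss is possible and unprotected, not prescribed, and only withdrawals before Day 7 matter for the primary endpoint.

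**Mortality.** A reader might extend the point to mortality. That is not supported. All-cause mortality draws on four CRFs (SAP 9.2.7), death is analysed using all available information (SAP 9.2.1), serious events are documented through Day 56 (Protocol 9.6), and a captured death before Day 7 scores 7.

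**Non-compliance.** Nothing in Protocol 11.3 ties it to clinical status. It is a second route to missing scores, not evidence of informative loss.

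**Exploratory trial.** No power is claimed, and SAP 4.1 presents p-values for information only. This limits the severity but does not remove the point.

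**Conclusion.** The point holds in a limited form. An investigator code-break, tied to clinical emergencies, forces withdrawal from a single-infusion study. Nothing secures the Day 7 score afterwards, and the SAP neither imputes it nor examines its absence. Day 7 scores may therefore be missing informatively.

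Bias in the treatment comparison is a further step that the documents do not establish. It needs loss that differs between arms. That is plausible: in the first challenge-study cohort, given no pretreatment, 6 of 7 VIS410 subjects and none of 5 placebo subjects had moderate to severe gastrointestinal events (Protocol 1.3.2.2). But all subjects here receive pretreatment, and no code-break rate is given.

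Under the assumptions above, 1 to 4 one-sided losses shift a null OR to between 0.94 and 0.76 for one arm, or 0.97 and 0.88 pooled. None of these shifts approaches significance, and equal loss produces none. This is a cheap improvement, not a flaw that undermines the trial.

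**What to change.** - **Protocol 10.2:** replace compulsory study withdrawal after an investigator or site code-break with continued scheduled assessments (ordinal scale through Day 14, vital status through Day 56) unless consent is withdrawn. Record the date of unblinding.
- **Protocol 11.3:** state that non-compliance alone does not end outcome collection. Leave the safety-based ground for withdrawal unchanged; nothing here gives a reason to alter it.
- **SAP 9.1:** report by arm the number of missing Day 7 scores and the number recorded after unblinding. Add a sensitivity analysis for each: one for missing Day 7 scores, one for scores assigned after the code was broken.

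The cost is protocol and SAP wording plus one date to capture. The downside is that a few later scores will be assigned by unblinded staff; the flag and the second sensitivity analysis show whether they matter.
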